### **8.3 Data Safety Monitoring Board**

The DSMB, appointed by the NHGRI, will be responsible for providing recommendations regarding the conduct of the study and guidance to ensure the safety and well-being of participants. The DSMB will meet semi-annually. A DSMB Charter will be developed detailing the procedures to be followed. A Data and Safety Monitoring Plan and a separate DSMB statistical analysis plan (SAP) will be developed in collaboration with the IGNITE PTN, IGNITE PTN CC, and NHGRI, and enacted by the DSMB.

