## **10. STATISTICAL ANALYSIS PLAN AND SAMPLE SIZE**

### **10.1 Sample Size Determination**

All trials power analyses are based on a modified intent to treat analysis, comparing the subset of intervention participants with have an actionable phenotype to the subset of control participants with an actionable phenotype. Effect sizes used to estimate power are based on prior studies of pain and depression pharmacogenetic testing and described below for each trial and shown in Table 8. Several steps were taken to generate a conservative sample size estimate. First, the power requirement was set to 90%. Second, sample sizes are adjusted for a 10% drop-out (for which UF has data from several studies that this is a good estimate). Third, slightly smaller effect sizes than what was observed in prior studies was used. Finally, sample size calculations are based on an alpha of 0.049, to allow one interim analysis with an alpha of 0.001 in each study.

Due to the study design and the delay in the control arm to obtaining the genotyping results required determine the actionable phenotype subgroup assignment, it is not feasible to directly monitor the number of randomized participants in the actionable subgroup for the enrollment stopping rule. Alternatively, the observed trial specific actionable phenotype percentages and the corresponding trial specific total enrollment targets will be used to identify when enrollment can conclude for a fully powered mITT study.

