**Table 9. Sample size calculations**

Sample size calculations for each trial, assuming an alpha of 0.049 to allow for one interim analysis

Study	Assumed Actionable Phenotype	Total N	Completed N (90% assumed)	Intervention	Usual Care	Intervention: Actionable Phenotype	Usual Care: Actionable Phenotype	Effect Size	Power
Acute Pain (CYP2D6 IM/PM)	18% (15%-24%)	2,020 (2424-1516)	1,690* (2028 - 1268)	845 (1014 - 634)	845 (1014 - 634)	152	152	0.375	90.00%
Chronic Pain (CYP2D6)	30% (24% - 33%)	994 (906 - 1244)	894 (814-1118)	447 (407-559)	447 (407-559)	134	134	0.4	90.00%
IM/PM)									
Depression (CYP2D6 or CYP2C19 PM/UM)	40% (up to 60%)	1,508 (1006)	1,356 (904)	678 (452)	678 (452)	271	271	0.28	90.00%
Total		4,522	3,940	1,970	1,970	557	557		

\*Accounts for an additional 7% of participants not completing surgery

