### **10.4 Analysis of the Primary Endpoint**

#### Acute Pain

To determine the effect of genotype-guided drug therapy on pain control in acute pain participants, we will conduct a subset analysis comparing SIA scores at 10-days post-surgery in the Intervention group subset with CYP2D6 IM or PM phenotypes to the Control group subset with CYP2D6 IM or PM phenotypes. Participants that have other CYP2D6 phenotypes will not be included. The 10-day post-surgery SIA scores of the Intervention CYP2D6 IM/PM group will be compared to the 10-day post-surgery SIA scores of the Control CYP2D6 IM/PM group using a two-sided two-sample t-test or Mann Whitney test, as appropriate, with a type 1 error of 0.049. This primary analysis will be conducted as a modified intent-to-treat analysis, with participants analyzed and endpoints attributed according to the treatment arm to which the participants were randomized, regardless of subsequent crossover or post-randomization medical care.

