#### **10.7 Interim Analyses**

A single specified interim analysis is planned for each trial. To account for repeated significance testing of the accumulating data, the group sequential method of Lan and DeMets will be used as a guide for

interpreting this interim analysis. Monitoring boundaries for the primary endpoint will be based on a two-sided symmetric O'Brien-Fleming type spending function with an overall two-sided significance level of  $\alpha=0.05$ . The O'Brien-Fleming approach requires large critical values early in the study but relaxes (i.e., decreases) the critical value as the trial progresses.

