#### Depression

The interim analysis of the depression primary endpoint, depression control at 3 months post return of PGx testing result to providers, will compare the participants with *CYP2D6* PM/UM or *CYP2C19* PM, RM and UM phenotypes in the Control arm to the participants with *CYP2D6* PM/UM or *CYP2C19* PM/RM/UM phenotypes in the intervention arm.

The primary analysis is a modified intent to treat design and the analytical subgroup is defined by the results of the PGx testing. Because the drug metabolizer phenotypes for participants in the Control arm is determined around the time of the 6-month follow up assessments for all trials (Acute Pain, Chronic Pain, and Depression), only participants that have completed their 6-month assessments will be included in the interim analysis. To account for the delays in receiving genetic testing results, the interim analysis will be targeted to occur when approximately 50% of the participants have completed their 6-month assessments. If the interim analysis does not propose stopping for efficacy (p-value  $<0.0003$  and the intervention has the larger reduction in the primary endpoints), then the conditional power to detect a significant result at the end of the trial will be estimated. The conditional power will be presented to the DSMB to facilitate discussion of whether the trial should be stopped for futility.

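### The interim efficacy threshold in Section 10.7 (p<0.0003) is about ten times stricter than the O'Brien-Fleming-type boundary the same section names (p about 0.0031 at 50% information), and the text does not say which governs

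*Combined protocol and SAP*

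**What the plan says.** The opening paragraph of Section 10.7 plans one interim analysis per trial. It says "the group sequential method of Lan and DeMets will be used as a guide for" interpreting the interim result, and then: "Monitoring boundaries for the primary endpoint will be based on a two-sided symmetric O'Brien-Fleming type spending function", with an overall two-sided level of 0.05.

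The closing paragraph of 10.7 stands under the Depression subheading but is worded for all three trials. On timing it says "the interim analysis will be targeted to occur when approximately 50% of the participants have completed their 6-month assessments". It then gives the efficacy criterion in parentheses: a p-value "<0.0003$ and the intervention has the larger reduction in the primary endpoints". If that is not met, conditional power goes to the DSMB for a futility discussion.

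Section 10.1 has another interim figure: "sample size calculations are based on an alpha of 0.049, to allow one interim analysis with an alpha of 0.001 in each study". Section 10.4 tests each trial's primary endpoint at the final level, for acute pain "as appropriate, with a type 1 error of 0.049", and the same level applies in chronic pain and depression.

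Section 8.3 says "a separate DSMB statistical analysis plan (SAP) will be developed", and Section 10.2 refers to separate detailed SAPs for each trial. Those documents are not available here.

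**The concern.** A spending function, an overall alpha and an information fraction together fix the interim boundary. Section 10.7 gives the first two and a target for the third, then prints a number that does not follow from them. If the interim p favours the intervention and lies between 0.0003 and about 0.0031, the named function has been crossed and the printed criterion has not been met.

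The opening paragraph does not itself order a stop, so someone working from 10.7 alone has two benchmarks. Unless the DSMB SAP already fixes one, the choice could be made after the p-value is known. The final significance level also depends on the answer, because a fixed 0.049 suits some interim rules at any likely fraction and the spending boundary only at some fractions.

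**Working it through.** **Inputs.** From 10.7: overall two-sided alpha 0.05, O'Brien-Fleming-type spending, one look at about 50%. From 10.1 and 10.4: final level 0.049, power 90%. From 10.1 and Table 9: 152, 134 and 271 analysable participants per arm (totals 304, 268, 542) for standardized effects 0.375, 0.40 and 0.28.

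**The plan's own sample sizes.** A normal-approximation calculation at alpha 0.049 and 90% power gives 151, 133 and 270 per arm, against the stated 152, 134 and 271. Noncentral-t power at the stated sizes is 90.1 to 90.2%. The design figures reproduce.

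**The named boundary.** At a first look, the nominal two-sided p equals the alpha spent:

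alpha(t) = 4 × [1 − Φ(z(0.9875)/√t)], with z(0.9875) = 2.2414.

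At t = 0.50, 2.2414/√0.50 = 3.170 and alpha(0.50) = 0.00305, so the boundary is |Z| = 2.963. The ratio to the printed number is 0.00305/0.0003 = 10.2. The matching final level is 0.0490.

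| Information fraction t | Interim p from named function | Ratio to 0.0003 |
|---|---|---|
| 0.35 | 0.0003 | 1.0 |
| 0.40 | 0.0008 | 2.6 |
| 0.45 | 0.0017 | 5.6 |
| 0.50 | 0.0031 | 10.2 |
| 0.55 | 0.0050 | 16.7 |
| 0.60 | 0.0076 | 25.4 |

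Inverting the function, 0.0003 corresponds to t = 0.350, 0.001 to t = 0.415 and 0.003 to t = 0.498. Other conventions at t = 0.50 do not rescue the printed number: classic two-look O'Brien-Fleming gives 0.0052, the alternative spending formula 2 × [1 − Φ(1.96/√t)] gives 0.0056, and overall alpha 0.049 gives 0.0029.

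**What 50% of participants could mean.** The information fraction is analysable actionable-phenotype participants divided by 304, 268 or 542.
- Half of Table 9's Total N, all with the endpoint and the planned actionable share: 0.5 × 2020/1690 = 0.598 (acute pain), 0.5 × 994/894 = 0.556 (chronic pain), 0.5 × 1508/1356 = 0.556 (depression). The boundary is then 0.0075, 0.0053 and 0.0053.
- Half of the synopsis targets (1730, 985, 1540) at 18%, 30% and 40% actionable: 0.5 × 1730 × 0.18/304 = 0.512; 0.5 × 985 × 0.30/268 = 0.551; 0.5 × 1540 × 0.40/542 = 0.568. Boundary 0.0035, 0.0051 and 0.0059.
- The same after planned attrition (× 1690/2020 for acute pain, × 0.9 for the others): 0.428, 0.496 and 0.511. Boundary 0.0012, 0.0029 and 0.0034.

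On each of these readings the named boundary is at least four times 0.0003.

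**Chance of crossing in favour of the intervention.** The final-analysis drift is z(0.9755) + z(0.90) = 3.250, so the interim mean of Z at t = 0.50 is 3.250 × √0.50 = 2.298. The crossing probability is 1 − Φ(critical value − 2.298):
- 0.0003 (critical value 3.615): 0.094
- 0.001 (3.291): 0.161
- 0.00305 (2.963): 0.253

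The gap between the two benchmarks in 10.7 is 0.253 − 0.094 = 0.159. At three-quarters, half and none of the design effect it is 0.078, 0.028 and 0.001. At the full effect it is 0.037 at t = 0.40 and 0.304 at t = 0.60.

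**Observed standardized difference needed at t = 0.50**, z × √(2/n) with n = 76, 67 and 135.5 per arm, for 0.00305 against 0.0003: acute pain 0.48 vs 0.59, chronic pain 0.51 vs 0.62, depression 0.36 vs 0.44.

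**Overall two-sided type I error with the final test at 0.049** (bivariate normal, correlation √t):

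| Interim rule | t = 0.35 | t = 0.50 | t = 0.55 | t = 0.60 |
|---|---|---|---|---|
| Fixed 0.0003 | 0.0491 | 0.0490 | 0.0490 | 0.0490 |
| Fixed 0.001 | 0.0494 | 0.0492 | 0.0492 | 0.0491 |
| Named function | 0.0491 | 0.0500 | 0.0506 | 0.0514 |

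With the named function, the final level that holds overall error at 0.05 is 0.0490 at t = 0.50, 0.0484 at 0.55, 0.0482 at 0.56 and 0.0476 at 0.60. Power at the planned N is then 90.1%, 90.0%, 90.0% and 89.9%.

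**The case against.** The strongest reply is that the text does settle the matter: Lan-DeMets is only a guide, and the specific p-value further down is the operative rule, chosen to be conservative. That reading is possible. But the sentence after the guide wording says the boundaries will rest on the spending function, and nothing marks 0.0003 as a deliberate departure. The final 0.049 does not decide it either: it is what the named function requires at 50% information, and it is also 0.05 − 0.001.

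A second reply is that the size of the mismatch depends on the information fraction. That is right. The mismatch vanishes near 35%, and the ratio runs from 2.6 at 40% to 25 at 60%. Control-arm phenotypes become known only around six months, so late results could lower the usable fraction. Still, every reading worked through above leaves the boundary well above 0.0003.

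Third, the practical harm is small. A fixed 0.0003 with a final 0.049 protects the type I error and leaves N alone, and the 16% applies only if the full design effect is true. This stands, and it limits the point to early stopping and a minor dependence of the final level.

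Fourth, the DSMB SAP or the trial SAPs may already fix one rule. They may; the conflict in Section 10.7 would remain.

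**Conclusion.** The concern holds. The printed criterion does not follow from the boundary that Section 10.7 names at the timing it sets: 0.0003 against 0.00305 at 50% information, a factor of about ten. Section 10.1's 0.001 is a sample-size statement rather than a stopping rule, but it matches neither.

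Under the design effect at 50% information, each trial has about a 16% chance of an interim p on which the two benchmarks disagree. This rests on the normal approximation, the planned effect sizes and a true fraction near 50%. Type I error is not inflated under either fixed threshold. Under the named function, a fixed final 0.049 gives 0.0506 at 55% information and 0.0514 at 60%. This should be fixed, but it does not undermine the design.

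**What to change.** Ask the sponsor whether 0.0003 is a slip for 0.003, which fits the named function at 49.8% information; the documents cannot confirm this. The answer is needed before interim results are seen; the documents do not say whether the look has taken place. Then state one governing rule in the same words in 10.1, 10.7 and the DSMB SAP:

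- **(a) Spending function governs.** Define the information fraction as actionable-phenotype participants in the interim who have the primary endpoint, divided by 304, 268 or 542. Give p<0.0031 as the illustration at 50%. Recompute the final level from the actual fraction (0.0490 at 50%, about 0.0482 at 56%, 0.0476 at 60%) in place of a fixed 0.049.
- **(b) Fixed threshold governs.** State 0.0003 (or 0.001) as deliberately stricter, remove the spending-function statement, and keep the final 0.049.

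The cost is wording only. N and the Table 9 counts do not change. Option (a) also needs Section 10.4 to let the final level follow the actual fraction. If the look falls at 55 to 60% information, that level drops to about 0.0484 to 0.0476, with power of 90.0 to 89.9% at the planned N.

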### **10.8 Handling of Missing Data**

For all primary and secondary statistical analyses described above, multiple imputation will be used for all missing values except those due to participant death. To ensure that the missing at random assumption for multiple imputation is valid, we will compare baseline pain or depression scores and other patient characteristics in those lost to follow up to participants retained on their randomization assignment. We will also do sensitivity analyses where we compare results obtained with multiple imputation to those obtained without imputation. Missing values due to death will not be imputed and will therefore not be included in the analyses. For exploratory repeated measures analyses, missing data are easily handled as long as the missing at random assumption is valid. However, the missing at random assumption cannot be tested. Accordingly, for exploratory analyses using repeated measures mixed models, we will also conduct a sensitivity analysis where missing values are imputed using multiple imputation. The results with and without multiple imputation will be compared. More complete details of the handling of missing values under different circumstances will be described in the SAP.

### **10.9 Multiplicity**

With the primary and various secondary endpoints that have been outlined, there is a multiplicity of analyses to be performed, which leads to an increased probability that at least one of the comparisons could be "significant" by chance. Adjusting for the effects of the repeated significance testing for the

multiplicity of secondary endpoints would require that very small significance levels be used for every comparison. Therefore, rather than adjusting for multiple comparisons, we will be conservative in the interpretation of the analyses, considering the degree of significance, and looking for consistency across endpoints. The nominal (unadjusted) p-value for each comparison will be reported to aid in the overall interpretation. We have also prespecified the primary and secondary outcome variables to avoid over-interpretation of strictly exploratory comparisons.

## 11. DATA MANAGEMENT

### 11.1 Data Entry and Record Keeping

ADOPT PGx data sources include: data collected from participant surveys, genetic testing results, data from the EHR, and CMS billing records. Data will be entered into a REDCap database maintained by the CC by trained and qualified personnel at each clinical site for baseline and follow-up assessments and by the UF call center for follow-up assessments. Site staff will receive training on the use of the REDCap database. After staff are trained, they will receive a unique user identification and password to access data entry forms for their site. Access codes should not be shared and are non-transferable.

Laboratories will transfer genetic testing results to the IGNITE PTN CC and follow standard site-specific return of results procedures for providers. The genotype and result (i.e. metabolizer phenotype) for each participant will then be imported to the participant's study database record from laboratory produced output files. The accuracy of the import of laboratory results will be verified by comparing the results recorded in the study database to an external record of the result for a subset of the study participants. See MOP for details.

Sites will extract the relevant data from their EHR (see Section 7.7) and transfer of those data to the IGNITE PTN CC following procedures that will be specified in the MOP. Briefly, sites will be given a list of trial-specific information to extract for their ADOPT PGx participants, a common format that data should be converted to, and procedures for secure file transfer to the CC.

### 11.2 Data Element Definitions

Clinically significant pain reduction: Whether or not the pain reduction score is  $\leq 0.7$ . If the pain reduction score is  $\leq 0.7$ , clinically significant pain reduction is achieved, if pain reduction scores is  $> 0.7$ , clinically significant pain reduction is not achieved.

Depression symptom control: The change in the PROMIS Emotional Distress - Depression 8b or PROIMIS pediatric Depression 8a survey depression score from baseline to time t.

Depression remission: A. Whether or not the summed raw PROMIS emotional distress depression 8b survey responses are  $\leq 16$ , which is equivalent to the participant responding “rarely” or “never” to most or all of the PROMIS emotional distress - depression 8b survey questions. B. Whether or not the PHQ-8 scores are  $\leq 4$ , which is equivalent to depression severity being none-mild.

Depression (PHQ-8) score: The sum of the responses to the PHQ-8 survey, range from 0 to 24.

Depression (T) score: The T-score converted summed responses to the PROMIS emotional distress depression 8b survey. The T-score conversion is centered around 50 with standard deviation of 10.

Depression severity: The depression score converted to depression severity (none, mild, moderate, severe) based on the scoring guide for the PROMIS emotional distress depression 8b survey.

Medication adherence: The scored responses to the Voils Medication Adherence survey.

Medication concordance: Whether or not the medication the participant is prescribed after the intervention is concordant with the participants CYP2D6 and, for the depression trial, CYP2C19 phenotype.

Medication side effects severity burden: (Depression only) The sum of the scored severity (none = 0, mild = 1, moderate = 2, severe = 3) for common SSRI side effects.

Opioid misuse score: The T-score converted summed responses to the PROMIS prescription medication misuse 7a survey. The T-score conversion is centered around 50 with standard deviation of 10.

Opioid persistence: Defined as  $\geq 1$  opioid prescription refill between 90 days and 180 days after the surgical procedure.

Opioid usage: The average daily morphine equivalents in mg (MED) in past 7 days. MEDs will be calculated using data from the opioid usage survey.

Overall well-being: Defined as the T-score converted summed responses to the PROMIS 43/PROMIS 37 pediatrics survey. The T-score conversion is centered around 50 with standard deviation of 10.

Pain control: The difference in pain intensity score at follow-up time t and the baseline pain intensity score.

Pain intensity score: The mean of average pain in the last 7 days, current pain, and worst pain in the last 7 days. Average pain, current pain, and worst pain will be collected using the 3-question PROMIS pain intensity scale.

Pain reduction score: The ratio of the pain intensity score (derived from the PROMIS pain intensity survey) at follow-up time t to the baseline pain intensity score.

Silverman integrative analgesic assessment (SIA) score: This is an integrated measure of pain and opioid usage, calculated as follows: pain and opioid usage are ranked, the ranks are converted to percentiles and linearly transformed such that the scores are centered at 0 and range -100 to 100. The pain scores and opioid usage transformed percentiles are summed to generate the SIA score that ranges -200 to 200. Negative values indicate low pain with minimal opioid usage, while positive values indicate higher pain with higher opioid usage. See Appendix A for additional details and supporting rationale.

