##### Acute pain

1. Pain intensity at 10 days post-surgery
2. Opioid usage at 10 days post-surgery
3. Prescription pain medication misuse score at 3-months post-surgery
4. Mobility at 1-month post-surgery
5. Opioid persistence 6 months post-surgery

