## Clinical Decisions Support / Clinical Recommendations

### Acute and Chronic Pain

Standardized clinical consult notes with or without pharmacogenetics expert consultations will be generated based on the genotype-inferred phenotype, and in the case of drugs including *CYP2D6* guidance, will include consideration of drug interactions.

For *CYP2D6*, those taking concomitantly a strong *CYP2D6* inhibitor (as defined by FDA guidance on drug interactions[28]) will be considered to have been pheno-converted to a PM and recommendations will be consistent with that for a PM. Examples of strong inhibitors include, but are not limited to: bupropion, fluoxetine and paroxetine. Moderate inhibitors include, but are not limited to: duloxetine and mirabegron and reduce *CYP2D6* activity scores by 50%, and thus the inferred phenotype will be based on the genotype activity score x 0.5. Activity scores that align with a given phenotype, and which will ultimately will be based on genotype and drug interaction data, are shown in Tables 2 and 3. A full list of strong and moderate inhibitors can be found in Appendix C.

While we will not be including oxycodone as a drug on which we will make recommendations in IMs and PMs, based on UF data and other data in the literature that make the importance of *CYP2D6* for the pain response unclear, there are data that suggest that *CYP2D6* UMs can have significant toxicities (especially respiratory depression).[1, 29-31] Thus, oxycodone will be a drug for which we will make strong recommendations about avoiding use in UMs.

Using a standardized consult note/CDS or pharmacogenetics expert consultation, recommendations will be made to avoid tramadol, hydrocodone, or codeine in PMs, IMs, and UMs and to use an alternative opioid (e.g. morphine, hydromorphone) or non-opioid (e.g. NSAID), as noted in Table 5. Consideration of tramadol as the first line opioid will be recommended for NMs. While not part of the primary hypothesis, for safety reasons, avoidance of oxycodone will also be recommended in UMs.

Additionally, where possible, the CDS will include a provider alert for actionable phenotypes, triggered when a relevant opioid medication is ordered that indicates the participant's genetic results, the predicted phenotype, other considerations, and treatment recommendations.

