**Acute pain specific health care utilization** – A participant completed survey of hospital length of stay for the surgical admission, administered at 10 days post-surgery.

**Opioid side effects** – A participant completed survey of common opioid side effects experienced and the extent to which those side effects bothered the participant. This survey will be administered at baseline, 10 days, 1-month, 3-months, and 6-months post-surgery.

**Opioid persistence** - Whether or not the participant had an opioid prescription refill 90 – 180 days post-surgery. This survey will be administered to participants at 6 months post-surgery.

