## 7.8 Data Collection from the Electronic Health Record

Data collected from the local EHR will include prescription information and encounters including clinic visits, hospitalizations, and emergency department visits and associated diagnoses for the study interval time-zero through six-month follow up. Sites will extract data using prespecified programmatic algorithms, site-developed algorithms, and/or manual chart abstractions. EHR query results will be sent to the IGNITE PTN CC via secure data transfer and formatted for consistency across sites. Details for the EHR elements and transfer process will be provided in the MOP.

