### Acute Pain

The effect of genotype-guided opioid therapy on secondary endpoints pain intensity, opioid usage, opioid misuse score, and mobility score will be assessed by comparing the Intervention group subset with CYP2D6 IM or PM phenotypes to the Control group subset with CYP2D6 IM or PM phenotypes using a two-sided two-sample t-test or Mann Whitney test, as appropriate, with a type 1 error of 0.05. The effect of genotype guided opioid therapy on the secondary endpoint opioid persistence will be assessed by comparing the Intervention group subset with CYP2D6 IM or PM phenotypes the Control group subset with CYP2D6 IM or PM phenotypes using a test of two-proportions with an alpha of 0.05. Participants with other CYP2D6 phenotypes will not be included in these analyses.

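### Opioid persistence counts only a prescription refill on days 90 to 180, so continued use supplied by new prescriptions goes uncounted

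*Combined protocol and SAP*

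**What the plan says.** Opioid persistence is the fifth acute pain secondary endpoint, listed in section 3.2 as "Opioid persistence 6 months post-surgery".

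- **Definition (11.2):** at least one "opioid prescription refill between 90 days and 180 days after the surgical procedure".
- **Survey (7.3, Acute Pain):** "Whether or not the participant had an opioid prescription refill" in that same window; "This survey will be administered to participants at 6 months post-surgery".
- **Source and timing (Table 8):** a custom survey only, at 6 months ± 14 days.
- **Analysis (10.5):** intervention against control among CYP2D6 IM or PM participants, "using a test of two-proportions with an alpha of 0.05".
- **Advice in that subset (7.1 and Table 5):** the intervention arm's decision support recommends avoiding tramadol, hydrocodone and codeine in favour of another opioid or a non-opioid. Control providers do not receive the study's results before 6 months.
- **Other prescription data:** section 7.8 states "Data collected from the local EHR will include prescription information and encounters", from time zero to the six-month follow-up. Table 8 adds Medicare and Medicaid billing records for filled prescriptions. Neither is named as a source for opioid persistence.

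**The concern.** Persistence is meant to show who is still being supplied with opioids three to six months after surgery. A refill is only one way of being supplied. A participant given a new opioid prescription at day 120 is still receiving opioids, but the rule as written scores that person as not persistent. Nothing in the documents says that a new prescription counts.

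The first consequence is that persistence is under-counted in both arms, which shrinks any true difference in rates and costs power. The second is a possibility only. The intervention acts on which drug is prescribed, and the endpoint depends on how supply is renewed. If the renewal route varied by drug, the share of persistent users captured could differ by arm.

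**Working it through.** **1. What the word covers.** The definition and the survey description both say refill, and neither defines it. Elsewhere the protocol keeps the terms apart. The opioid consumption questionnaire (7.3) lists pills dispensed and refills as separate items. The note on follow-up timing (7.3) gives a new prescription order as an event of its own. Table 8 speaks of filled prescriptions. So refill cannot safely be taken to mean any fill.

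**2. Survey timing.** Six months is about 182 days, and 182 − 14 = 168. A survey at the early edge leaves 180 − 168 = 12 days of a window of about 90 days unobserved. Acute pain follow-up is timed from surgery in both arms (7.3), so nothing in the design makes this differ by arm.

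**3. The plan's sample size.** Section 10.1 gives 152 actionable participants per arm for the SIA score (effect size 0.375, two-sided alpha 0.049, power 90%). The normal approximation gives n = 2(1.969 + 1.282)² / 0.375² ≈ 150.2, so 151 per arm. At 152 the noncentral-t power is 90.1%. The figure reproduces. The documents give no rate, effect size or power for opioid persistence, so every rate below is an assumption.

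**4. Equal under-capture in both arms.** Let c be the share of truly persistent users who have a refill. The recorded rate is c × the true rate. With p̄ the mean of the two recorded rates and d their difference:

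- SE₀ = √[2p̄(1 − p̄)/152]
- SE₁ = √{[p₁(1 − p₁) + p₂(1 − p₂)]/152}
- power ≈ Φ[(d − 1.96·SE₀)/SE₁]

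Example at c = 1, assumed true rates 20% and 10%: SE₀ = √(2 × 0.15 × 0.85/152) = 0.0410; SE₁ = √[(0.16 + 0.09)/152] = 0.0406; Φ[(0.10 − 0.0803)/0.0406] = Φ(0.49) = 0.69.

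| Capture c | Recorded rates | Difference | Power |
|---|---|---|---|
| 100% | 20% v 10% | 10 points | 69% |
| 80% | 16% v 8% | 8 points | 57% |
| 60% | 12% v 6% | 6 points | 45% |

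The risk ratio stays at 0.5 and the type I error at 5%. The loss is in the absolute difference and in power.

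**5. Unequal capture, no true difference (illustration only).** The same test gives these rejection rates against the nominal 5%:

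| True persistence, both arms | Capture 90% control / 70% intervention | Capture 90% control / 50% intervention |
|---|---|---|
| 5% | 7% | 16% |
| 10% | 10% | 28% |
| 20% | 16% | 52% |
| 30% | 23% | 73% |

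The apparent risk ratios are 0.70/0.90 = 0.78 and 0.50/0.90 = 0.56. Swapping the arms gives the same rejection rates with ratios of 1.29 and 1.80. Nothing in the documents says which direction applies, or whether capture differs at all.

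**The case against.** **The survey wording is not shown.** Section 7.3 gives one line of description and Table 8 says only that the survey is custom. In lay use a refill can mean any further supply. If the item asks about any opioid fill, the gap is one of wording in the protocol. This stands as a limit on what can be concluded, but it does not make the written definition adequate: the text says refill only, and participants asked about a refill may reasonably answer no.

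**Bias in favour of the intervention is not shown.** A reader might infer that the definition makes the intervention look better because the opioids it steers towards are renewed by new prescriptions. The documents do not support that:

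- They contain no renewal rules by drug and no split of refills and new prescriptions by arm.
- The advice is a recommendation that includes non-opioids, and the physician decides (6.5). A move to a non-opioid would be a true fall in persistence.
- Oxycodone is listed as acceptable for IM and PM participants in Table 5, and control prescribing is usual care, so both arms can use the same drugs.
- A drug chosen around surgery could still be refilled on days 90 to 180.

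This objection stands in full.

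**The stakes are limited.** There are five acute pain secondary endpoints. Section 10.9 promises cautious interpretation, and section 10.2 defers detail to a separate SAP for each trial. This bears on severity and not on whether the definition should be corrected.

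**The remedy has faults.** Counting new prescriptions will include some unrelated opioid courses, such as one after a second procedure. Local EHR data can miss outside prescribers. Changing the item mid-trial could mix two versions of the endpoint. All three are fair and are addressed in the fix.

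**Conclusion.** The point holds as a measurement weakness of minor severity. As written, opioid persistence misses continued use supplied by new prescriptions, and an early survey can miss up to about 12 further days. Persistence is under-counted and power is lost. The illustrated fall from 69% to 57% or 45% rests on assumed true rates of 20% and 10%, assumed capture of 80% or 60%, and 152 per arm; the actual capture is unknown.

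Different capture by arm is a possibility that follows from the design, not a demonstrated bias, and neither its size nor its direction can be taken from the documents. The primary SIA score and opioid usage at 10 days do not use this definition.

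**What to change.** 1. In section 11.2, define opioid persistence as at least one opioid prescription filled, new or refill, for any opioid, on days 90 to 180 after surgery. Bring section 7.3 and the survey item into line.
2. For participants already surveyed under the present item, do not pool their answers with answers to a revised item. Use the EHR prescription data, with claims where available, to derive the endpoint or to run a sensitivity analysis by arm. If it becomes the endpoint, derive it in the same way for everyone in the comparison.
3. Specify that the EHR extraction for this endpoint runs to day 180 after surgery, so that an early survey or follow-up contact does not shorten the window. State how a prescription that is recorded but not shown to be filled will be treated.

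The cost is one definition, one survey item and a short derivation rule in the acute pain SAP; the EHR data are already planned. Some unrelated new opioid courses will be counted, outside prescribers may be missed, and claims cover Medicare and Medicaid participants only. Reporting refills and new prescriptions separately by arm would show how much the definition matters. The sample size and the primary analysis do not change.
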